12.1.7 Hypertonia Assessment Tool (HAT)

The HAT is a clinical assessment tool developed to differentiate subtypes of hypertonia in the pediatric population. This scale contains 7 items and each item can be scored as 0 (negative) or 1 (positive). The results determine if a patient has spasticity, dystonia, rigidity, or mixed tone ([Jethwa et al, 2010](#)).

For this study, HAT will be performed on the study upper limb to ensure the presence of spasticity.

12.1.8 The Manual Ability Classification System (MACS)

The MACS provides a functional description of how a child with cerebral palsy uses his or her hands when handling objects in daily activities. This measure focuses on typical manual performances, not the maximal capacity ([Eliasson et al, 2006](#)); and is a description of function of both hands together. MACS should be conducted by asking someone who is familiar with the child, not by performing an assessment. The child's level of manual ability can be depicted by one of the following levels:

- I. Handles objects easily and successfully
- II. Handles most objects but with somewhat reduced quality and/or speed of achievement
- III. Handles objects with difficulty; needs help to prepare and/or modify activities
- IV. Handles a limited selection of easily managed objects in adapted situations
- V. Does not handle objects and has severely limited ability to perform even simple actions

While this scale is developed specifically for patients with cerebral palsy, it will be applied to the post-stroke patients in this study for screening purposes. Investigators will review patient's manual ability at the screening visit. Patients with MACS level I-IV will be eligible for the study.

12.1.9 Gross Motor Function Classification System – Expanded and Revised (GMFCS-E&R)

The GMFCS-E&R for cerebral palsy is based on self-initiated movement ([Palisano et al, 2007](#)). The emphasis of this scale is on sitting, transfers, and mobility, and focuses on determining which level best represents the child's present ability and limitations in gross motor function. Instead of reflecting what the child can do best (capability), this scale focuses on his or her usual performance in home, school, and community settings.

Five levels are included in this scale:

Level I	Walks without limitations
Level II	Walks with limitations
Level III	Walks using a hand-held mobility device
Level IV	Self-mobility with limitations; may use powered mobility
Level V	Transported in a manual wheelchair

Detailed descriptions are provided for each level of classification by age groups (before 2nd birthdays, between 2nd and 4th birthdays, between 4th and 6th birthdays, between 6th and 12th birthdays, and between 12th and 18th birthdays). While this scale is developed specifically for patients with cerebral palsy, it will also be applied to the post-stroke patients in this study for screening purposes. The investigator will assess the patient's motor function using GMFCS-E&R at the screening visit. Patients with GMFCS-E&R levels I to IV will be eligible for the study.

12.1.10 Modified Ashworth Scale - Bohannon (MAS-B)

The MAS-B will be used to evaluate spasticity based on grading the resistance encountered in a specific muscle group by means of passively moving a limb through its range of motion at a study-specified velocity. The resistance encountered to passive stretch is graded from 0 = no increase in muscle tone to 4 = affected part(s) rigid in flexion or extension ([Bohannon and Smith, 1987](#)). The same investigator should perform this measure at each visit, if possible.

- 0 No increase in muscle tone
- 1 Slight increase in muscle tone, manifested by a catch and release, or by minimal resistance at the end of the range of motion when the affected part(s) is moved in flexion or extension
- 1+ Slight increase in muscle tone, manifested by a catch, followed by minimal resistance throughout the remainder (less than half) of the range of motion
- 2 More marked increase in muscle tone through most of the range of motion, but affected part(s) easily moved. There can be a catch, but movement should be stiff through most of range.
- 3 Considerable increase in muscle tone, passive movement difficult
- 4 Affected part(s) rigid in flexion or extension

Please refer to the Study Procedure Manual for detailed instructions on performing the MAS-B on the elbow, wrist, and finger muscle groups.

12.1.11 Modified Tardieu Scale (MTS)

The MTS will be used to determine the passive range of movement at different movement velocities, V1 (as slow as possible) and V3 (as fast as possible), with the relative difference between a slow and a fast velocity passive stretch determining the dynamic component of the muscle contracture ([Love et al, 2001](#)).

At each visit, the same investigator (when possible) will measure 2 joint angles by goniometer: the R1 angle, which is the “angle of catch” after a fast velocity (V3) stretch, and the R2 angle, which is defined as the passive joint range of movement following a slow velocity (V1) stretch. The R2 – R1 value indicates the level of dynamic contracture in the joint. Measurements of R1 and R2 should be done at approximately the same time of day at each visit using a constant position for the affected study upper limb being evaluated. The R1 angle should be measured prior to the R2 angle.

Please refer to the Study Procedure Manual for detailed instructions on performing the MTS on the elbow, wrist, and finger muscle groups.

12.1.12 Goal Attainment Scale (GAS) by Physician

The GAS by Physician will be used to measure functional goal attainment relative to the effect of the study intervention. Goals should be specific, measurable, achievable and realistic, resource sensitive, and timed (SMART). At week -2, two goals will be selected by the patient and family in consultation with the physician investigator and/or treating therapist relative to the upper limb impairment due to spasticity. These goals will be confirmed at the day 1 visit. Two functional goals will be established for each patient: a functional active goal and a functional passive goal. After the functional goals (active and passive) are set, they should remain the same throughout the study. It is crucial to define all the levels of the goal. Goal achievement will be assessed by the physician investigator taking into consideration input from the treating therapist, caregiver, and/or patient.

The following scale will be used to evaluate the level of achievement of the 2 goals:

- 3 Worse than start
- 2 Equal to start: the patient's initial condition; no change
- 1 Less than expected: slight improvement, but below the defined therapeutic goal
- 0 Expected goal: attains the defined therapeutic goal
- +1 Somewhat more than expected: improvement slightly exceeds the defined therapeutic goal
- +2 Much more than expected: improvements clearly exceed the defined therapeutic goal

12.1.15 Clinical Global Impression of Overall Change (CGI) by Physician

Ideally, the CGI by Physician should be performed prior to administering the MAS-B and MTS to reduce the likelihood of the CGI being influenced by the spasticity evaluations. An alternative is to have different evaluators rate the CGI and perform the spasticity assessments (MAS-B and MTS). Whenever possible each procedure should be performed by the same evaluator for an individual patient throughout the trial. Study personnel should avoid reviewing or discussing the MAS-B, MTS, or CGI scores from previous visits when they are completing these assessments.

Each assessment should be evaluated relative to the patient's condition prior to entering the study. The physician investigator should make an assessment of the change (improvement or worsening) from baseline (day 1) taking into account the patient's clinical condition and severity of side effects. The investigator should choose a score that indicates his/her assessment about any therapeutic effects from the study intervention. Several factors can be considered when assigning a score including but not limited to assessment of any specific benefit/detriment to the patient, adverse events, risk/benefit of the study intervention, any effects on the patient's social and/or psychological status.

“How is the subject doing in his/her life since he/she received the study medication?”:

- 4 Very marked worsening
- 3 Marked worsening
- 2 Moderate worsening
- 1 Slight worsening
- 0 Unchanged
- +1 Slight improvement
- +2 Moderate improvement
- +3 Marked improvement
- +4 Very marked improvement

12.1.18 Columbia-Suicide Severity Rating Scale (C-SSRS)

The C-SSRS ([Posner et al, 2011](#)) is a semistructured interview designed to assess the severity and intensity of suicidal ideation, suicidal behavior, and non-suicidal self-injurious behavior over a specified time period (eg, prior year, since last visit). The measurement of suicidal ideation is based on 5 “yes” or “no” questions (plus a description if answered “yes”) arranged in order of increasing severity. If the patient answers “yes” to either question 1 or 2, the intensity of ideation will then be assessed in 5 additional questions relating to the frequency, duration, controllability, deterrents, and reasons for the most severe ideation. Suicidal behavior is then assessed by asking further questions to categorize the behaviors into actual, aborted, and interrupted attempts; preparatory behavior; and non-suicidal self-injurious behavior. The interview is used in full only if the initial questions are positive; this assessment is completed at all scheduled clinic visits at which other clinical assessments are to be carried out.

If any item(s) on the C-SSRS are answered with “yes”, a physician investigator must review patient’s responses in order to:

- a. at screening and baseline determine patient’s study eligibility and potential need for referral to a mental health professional, and
- b. during the study evaluate patient’s need for appropriate medical management such as referral to a mental health professional

A significant risk of suicide is defined as a “yes” in answer to: a) questions 4 or 5 on the suicidal ideation section; or b) any questions on any item in the suicidal behavior section.

This must be reported as a serious adverse event and followed up accordingly (see Sections 9.1.2 and 9.3 of the study protocol). Additionally, if a patient responds “yes” to any of the suicidal ideation questions 1 to 3, the investigator should apply clinical judgment to determine the need for reporting as an adverse event or serious adverse event and the need for any referral.

The C-SSRS is available in several versions designed for use in clinical trials. Appropriate versions of the scale will be used in this trial.

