7.3.4 Safety Analyses

Safety variables, including the incidence of adverse events, the incidence of suicide-related events using the C-SSRS (for patients \geq 6 years of age at day 1), laboratory test values and changes from baseline, as well as vital signs and their change from baseline, will be summarized by treatment group using the safety population. The Medical Dictionary for Regulatory Activities (MedDRA) nomenclature will be used to code adverse events and medical history. The incidence of adverse events (both pre-treatment events and treatment-emergent events) will be tabulated by primary system organ class and preferred term for each treatment group. Possible distant spread of toxin adverse events will be assessed using a standardized methodology.

Descriptive statistics will be presented for vital signs and numeric laboratory tests and the respective changes from baseline. All laboratory values will be presented by descriptive statistics. In addition, laboratory values outside the normal reference ranges for each patient at each applicable visit will be identified and evaluated against baseline via shift table analysis. Potentially clinically significant abnormal values may be identified or summarized descriptively.

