8.3.3 Visit 3: Day 1 (Randomization/Treatment)

- The following procedures must be performed prior to the study treatment:**
 - [REDACTED]
 - Note any update to medical and surgical history, if needed. Query patient/caregiver for any adverse events prior to study treatment.
 - Perform C-SSRS (for patients \geq 6 years of age at day 1).
 - For patients who are not eligible for the study (screen failures), depending on the reason(s) for screen failure, collect detailed information regarding spasticity, contracture, respiratory condition or functions associated with increased risk of aspiration, seizure, and epilepsy.
 - Obtain any update to concomitant medication use.
 - Obtain any information on new medical procedures or tests since the last visit.
 - Obtain vital signs (blood pressure, pulse rate, respiratory rate, and body temperature).
 - Obtain weight in kilograms.
 - Review the results of the screening safety laboratory tests.
 - Perform urine pregnancy test for all females of childbearing potential.
 - Assess spasticity in the elbow, wrist, and finger in the study limb using the MAS-B.
 - Perform MTS in the elbow, wrist, and finger in the study limb. Passive range of motion for the elbow, wrist, and finger can be performed during the MTS assessment in order to verify inclusion criteria.
 - Confirm the 2 goals selected and the definitions of patient-specific goal achievement using the GAS by Physician.

- [REDACTED]
- If applicable, counsel female patients and/or caregivers of childbearing potential regarding the importance of maintaining their agreed upon method of contraception throughout the study.
- Confirm patient continues to meet study inclusion and exclusion criteria.
- Identify principal muscle group and calculate the dose for study treatment using the dose calculation worksheet and dose verification eCRF.
- Access the IVRS/IWRS to randomize the patient and obtain a study medication kit number.
- Inform IDR that patient is qualified for the study treatment and send blinded dosing summary to the IDR for study drug preparation.
- Inject assigned study treatment as per protocol (see Section 5.9).
- Query patient/caregiver for any adverse events and related medication used or procedure performed.
- Remind patient/caregiver of the importance of the weekly OT session.
- Schedule the next visit.

8.3.4 Visits 4, 5, 6, and 7: Weeks 2, 4, 6, and 8 (Follow-up Visits)

- [REDACTED]
- [REDACTED]
- [REDACTED]
- [REDACTED]

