6.2 Treatment Emergent Adverse Events

Adverse events are collected both for the screening/baseline period prior to treatment (which are referred to as pre-treatment adverse events as cited in Section 4.6) and for the follow-up period after treatment is initiated.

A treatment-emergent adverse event (TEAE) is a post-baseline adverse event with onset after the initiation of study treatment or an adverse event with onset prior to study treatment that worsened in severity or became serious after the initiation of study treatment. The number and percentage of patients reporting each event will be summarized and presented for all events and tabulated by treatment groups (6 U/kg, 3 U/kg, and placebo) and overall as follows:

- i. By primary SOC and preferred term. At each level of summarization (overall, primary SOC, and preferred term) a patient will be counted once if he/she reports 1 or more experiences at that level.

- ii. By primary SOC, preferred term and severity. For a given adverse event of a patient, if more than 1 severity grade was reported, the worst severity grade will be included in the tabulation.

All treatment-related TEAEs (study drug-related and injection procedure-related TEAE) will be presented by primary SOC and preferred term. A listing of adverse events leading to discontinuation will also be provided.

The number and percentage of patients with any of the preferred terms will be summarized for each primary SOC and preferred term. All patients will be counted only once for each preferred term when multiple occurrences of the same preferred term are reported.

In addition, individual patient data listings (including adverse event listings that include the investigator verbatim terms and MedDRA lower level terms) will be provided.

Furthermore, the assessment of possible distant spread of toxin will be performed using the list of 39 MedDRA preferred terms (version 19.0 or its updated version as appropriate during the time of data analysis).

MedDRA Preferred Terms Evaluated for Possible Distant Spread of Toxin

Cardiac Disorders

Bradycardia

Eye Disorders

Accommodation disorder
Diplopia
Extraocular muscles paresis
Eyelid function disorder
Eyelid ptosis
Pupillary reflex impaired
Vision blurred

Gastrointestinal Disorders

Constipation
Dry mouth
Dysphagia
Ileus paralytic

Infections and Infestations

Botulism

Musculoskeletal and Connective Tissue Disorders

Muscular weakness

Nervous System Disorders

Bulbar palsy

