6.6 Columbia-Suicide Severity Rating Scale

Suicidality for age over 6 years will be assessed using the Columbia-Suicide Severity Rating Scale (C-SSRS), conducted at every assessment visit. Suicide-related events corresponding to the C-SSRS questions will be classified into the following 11 categories:

- Self-injurious behavior, no suicidal intent
- Suicidal ideation
 1. Wish to be dead
 2. Active: Nonspecific (no method, intent, or plan)
 3. Active: Method, but no intent or plan
 4. Active: Method and intent but no plan
 5. Active: Method, intent and plan
- Suicidal behavior
 1. Preparatory acts or behaviors
 2. Aborted attempt
 3. Interrupted attempt
 4. Suicide attempt
 5. Completed suicide

The number and percentage of patients with the above suicide-related events during treatment will be presented by treatment group. If a patient has more than one suicide-related event during an interval, the most severe event in increasing order listed above will be used.

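### The C-SSRS table in SAP 6.6 ignores the two pre-injection assessments, so it cannot separate persisting ideation from new or worsened ideation

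*Protocol*

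**What the plan says.** **Collection.** Protocol 12.1.18 says of the C-SSRS that "this assessment is completed at all scheduled clinic visits at which other clinical assessments are to be carried out". For children aged 6 or over at day 1, the visit lists place it at screening (8.3.1), at weeks 2, 4, 6 and 8 (8.3.4) and at week 12 or exit (8.3.5). On day 1 it falls under the instruction "The following procedures must be performed prior to the study treatment" (8.3.3). Each assessed child should therefore have two pre-injection results.

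**Entry.** In Protocol 12.1.18, significant risk means a yes to "questions 4 or 5 on the suicidal ideation section; or b) any questions on any item in the suicidal behavior section". Any yes at all requires a physician review, in order to "at screening and baseline determine patient’s study eligibility and potential need for referral to a mental health professional". For a yes to one "of the suicidal ideation questions 1 to 3, the investigator should apply clinical judgment to determine the need for reporting as an adverse event". The current text of exclusion criterion 29 is blacked out. The Amendment 2 summary (Protocol 12.5) indicates that it excludes children at significant risk of suicide.

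**Tabulation.** SAP 6.6 sorts events into 11 categories, among them the three milder ideation levels, and then states: "The number and percentage of patients with the above suicide-related events during treatment will be presented by treatment group". If a child has several events in an interval, the most severe is used. The section defines neither the treatment period nor the interval for this single-injection study. It has no pre-injection column, no shift table and no rule for new or worsened events.

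**Other safety data.** SAP 6.2 counts an event that began before treatment only if it is "an adverse event with onset prior to study treatment that worsened in severity or became serious after the initiation of study treatment". SAP 6.4 and 6.5 summarize laboratory values and vital signs with change from baseline. SAP 2.3 gives a general baseline definition, which 6.6 does not apply.

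**The concern.** The plan collects suicidality before and after injection but tabulates only what comes after. Some children may enter with mild ideation that simply continues. In the table by arm they look the same as children whose ideation began or deepened after injection.

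The table exists to show whether the drug is associated with suicidality. Few events are expected, so one or two persisting cases falling in one arm could suggest a signal, or mask one, and the table alone would not show which. The rest of the SAP's safety section refers findings to baseline; this table does not.

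**Working it through.** The documents state no C-SSRS rate, count or precision, so there is no plan figure to reproduce. The check is a reading of the text, followed by an illustration on assumed values.

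**1. One child traced through the rules.** Take a child who endorses the mildest ideation item at screening, on day 1 and at week 2, with no change.

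| Rule | Result for this child |
|---|---|
| Significant-risk definition, Protocol 12.1.18 | Not met; entry depends on the physician's review |
| C-SSRS table, SAP 6.6 | Counted as an event during treatment |
| TEAE rule, SAP 6.2, if recorded as an adverse event before injection | Not counted: neither worse nor newly serious |
| Change-from-baseline approach, SAP 6.4 and 6.5 | Would show no change |

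**2. Which rows are affected.** If criterion 29 follows the significant-risk definition, children with the higher ideation levels or any behavior item before injection are not randomized. The mixing is then confined to the three milder ideation rows. Within those rows, a child who moved from level 1 to level 3 cannot be told from one who was at level 3 throughout.

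**3. Illustration. Every input below is an assumption except 71.** Protocol 7.5 gives 71 completers per arm but not how many are aged 6 or over.

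- n, assessed children per arm: 40 to 71 (71 as if every completer were old enough)
- p, share with question 1 to 3 ideation before injection: 1 to 5%
- q, share of those endorsing it again after injection: 25 to 100%
- e, true new-onset rate in the remaining children: 1%

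Persisting cases per arm = n × p × q. New cases per arm = n × (1 − p) × e. Persisting share of all counted = pq / [pq + (1 − p)e].

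- Fewest persisting: 40 × 0.01 × 0.25 = 0.1 per arm. Most: 71 × 0.05 × 1 = 3.55 per arm.
- New cases: from 40 × 0.95 × 0.01 = 0.38 to 71 × 0.99 × 0.01 = 0.70 per arm.
- Lowest share: 0.0025 / (0.0025 + 0.0099) = 20%. Highest: 0.05 / (0.05 + 0.0095) = 84%.

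One child is 1/40 = 2.5 percentage points of an arm of 40, or 1/71 = 1.4 points of an arm of 71.

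**4. Chance imbalance with no drug effect.** Let persisting cases in two arms be independent binomial counts with common rate r = pq. The probability that the two counts differ by at least 2 is:

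| n per arm | r = 1% | r = 3% | r = 5% |
|---|---|---|---|
| 40 | 8.5% | 30.1% | 42.7% |
| 71 | 18.1% | 44.6% | 55.6% |

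Incomplete persistence lowers r and so lowers these figures.

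**The case against.** The case on the other side has real force.

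- **Eligibility.** A reader might infer that ideation at questions 1 to 3 does not bar entry. The documents do not go that far. Any yes goes to a physician's eligibility review, and criterion 29 and most other exclusions are blacked out. Only the absence of an automatic bar can be read from the visible text.
- **Incidence.** A reader might also infer that SAP 6.6 contradicts the protocol, because Protocol 7.3.4 promises "the incidence of suicide-related events using the C-SSRS" and incidence suggests new onset. The same section uses the word for adverse events that include those before treatment, so there is no contradiction.
- **Listings.** SAP 2.3 provides for listing all data except commonly expected results. A positive C-SSRS answer hardly falls under that exception, so a reader of the listings could follow each child from screening onward. It would be wrong to say that the planned output gives no way to tell; only the table fails to.
- **Adverse event route.** The severe categories must be reported as serious adverse events, and milder ideation may be reported on judgment. Reported events then follow the treatment-emergent rule. This leaves the C-SSRS table's own count unchanged.
- **Recall period.** Protocol 12.1.18 does not fix the C-SSRS version. If follow-up visits ask about the time since the last visit, a yes at week 2 is ideation that did occur after injection, and counting it is accurate. It is still not evidence of change.

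These points limit the consequence. They do not supply the missing comparison in the table by arm. The sentence on clinical judgment in Protocol 12.1.18 is not itself at fault; the gap is in SAP 6.6.

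**Conclusion.** The point holds as a minor reporting gap. As written, SAP 6.6 counts unchanged ideation that is endorsed again after injection, and its table cannot separate persisting from new or worsened cases.

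A reader might infer that the comparison between arms is biased. It is not, systematically: randomization balances pre-existing ideation in expectation, and no test is planned on this table. What remains is dilution of any true difference and chance imbalance at small counts. Efficacy results and the adverse event tables are unaffected.

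The size cannot be computed from the documents. The 20 to 84% persisting share rests wholly on the assumed rates and on the number of children assessed. The route into the trial for a child with mild ideation is inferred from Protocol 12.1.18 and the Amendment 2 summary, because criterion 29 cannot be read.

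**What to change.** In SAP 6.6:

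1. Define the pre-injection period (screening and day 1) and the post-injection period (all later assessments). State that the worst pre-injection category is used, because the general rule in SAP 2.3 would take only the last value.
2. Report by arm the worst pre-injection category.
3. Add by arm a count of children whose worst post-injection category is new or worse than their worst pre-injection category, or a shift table of the two. Show self-injury without suicidal intent on its own row: it is lowest in the SAP's severity order, so it could never count as worse than earlier ideation.
4. Use a comparable recall period before and after injection where the C-SSRS version allows. A long look-back at screening would raise the pre-injection category and hide new ideation.
5. Keep the planned all-events count as a row, and describe differences between arms from the new-or-worsened count.

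While the section is open, reconcile its age limit (over 6 years) with the limit in SAP section 6 and the protocol (6 years or older), since this sets the denominator.

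The cost is SAP wording and one extra table block. No new data are needed.
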